Ecological Momentary Assessment Procedure: EMA data will be collected through smartphones using the HIPAA compliant LifeData system (www.lifedatacorp.com) at Phase II 0, 2, and 4-month assessments. Consistent with protocols employed by Drs. [name] and Leahey⁷²⁻⁷⁶, each wave of EMA data collection will last 7 days with 4 prompts per day between the hours of 6:30 am and 10:00 pm. If participant schedule does not allow for data collection during this time window (e.g. night shift worker), the timing of the prompts will be adjusted. EMA prompts will be within 4 preprogrammed windows to ensure adequate spacing throughout the day. When prompted, participants will be instructed to stop what they are doing and complete a short electronic EMA sequence (3-5

minutes total). If signaled during an incompatible activity (e.g., driving), participants will be instructed to ignore the prompt. If no entry is made, the participant will receive up to 3 reminders. We anticipate that participants will answer between 80-85% of prompts based on prior research^{75,77}.

Executive function: Four aspects of executive function will be assessed at Phase II assessment clinic visits—working memory, inhibitory control, sensitivity to reward, and delayed discounting.

Working Memory: A N-back task will ask individuals to rapidly discern targets from foils by identifying whether the stimulus on the screen is the same as n trials previously. Stimuli will be presented for 1500ms or until the participant responds (25% targets). N-back tasks are sensitive to obesity-related cognitive dysfunction⁷⁸. Dependent variables include both discrimination rate and reaction time for correct trials.

Response Inhibition: Established go/no-go tasks will ask individuals to quickly respond to target stimuli when presented on the screen (75% go stimuli) and inhibit to other stimuli⁷⁹. Stimuli are presented for 500ms at varying 2000-4000ms inter-trial intervals. Such tasks are associated with eating behavior in overweight persons in other studies^{80,81}. Discrimination and reaction time will serve as dependent variables.

Risk taking: The well validated measure Iowa Gambling Task¹⁰³ will be used to assess risk taking. In this task participants select from card decks (on a computer screen) with different probabilities of gaining/losing different amounts of hypothetical money.

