Attentional Bias: measured by Dot Probe tasks will be used to assess attentional bias towards food⁸⁰. On these tasks, participants are asked to watch the screen while 2 images are briefly presented. A dot then appears and participants are asked to identify which side of the screen it was presented (i.e. left vs right) as quickly and accurately as they can. Both food and non-food pictures will be used and both discrimination and reaction time will be assessed. _____

Given that depression can negatively affect cognitive functioning⁹⁷, the Center for Epidemiologic Studies Depression Scale (CES-D)⁹⁸ will be used to account for contribution of mood symptoms to cognitive functioning scores. Given that this is a screening tool, participants will be given referrals for mental health treatment if they score in the clinical range (16 or above).

To clarify the independent contribution of DD and executive functioning on PA, the **Spot-the-Word test** will be used to estimate full-scale intelligence. It will be utilized as a covariate in analyses to clarify the relative contribution of global vs. specific cognitive abilities on outcomes. Spot-the-Word is a well validated test based on lexical decision making which is highly correlated with verbal intelligence. This test was normalized on a sample stratified by age and socio-economic status and is relatively resistant to the effects of age, brain damage, and stress (N=224).⁶⁴

Delayed Discounting. We will administer a clinic-based, adaptive computerized assessment of delayed discounting^{60,61}, at the start of weight loss maintenance and 1, 2, and 4 months later. This task asks participants to choose between less value now and greater value in the future (e.g. “would you rather have \$50 now or \$100 in two weeks”). A brief version of this task will be used for EMA assessment to capture the immediate effects of EFT on DD. The steepness of the DD curve will be examined across indifference points (i.e. when one opts for less sooner vs. now later across different time delays) to calculate a k discounting function.

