Power. Based on prior DD and EFT work^{31,34,39}, power is computed for an effect size (d) of 0.50. The computations assume an intraclass correlation (ICC) of 0.250 for the 4 time points clustered within each participant. The standard deviation is assumed to be the same in the two conditions. The criterion for significance (alpha) has been set at 0.05. The test is 2-tailed, which means that an effect in either direction will be interpreted. Given these assumptions, the study will have 82.1% power to yield a statistically significant result that will increase in one unit per number of individual covariate(s) included in the models. Accounting for 15% attrition, 15 more participants will be added, so a total of 160 participants will be enrolled in Phase I.

Analyses.

Primary hypothesis 1: WLM+FT will produce more engagement of DD and PA adherence. Descriptive statistics will be generated on all the demographic variables as well as mediators (DD), moderators

(environmental variables), covariates (WAIS-II) and outcomes (PA and weight). Differences between WLM-HT and WLM+FT will be assessed through chi-square tests (proportions) or Student's t-test (means) at each time point; if differences on any of the demographics are found at baseline, the variable will be used as a covariate in the main model. The main outcome, PA distribution data will be examined and if variables violate distributional assumptions of normality, will be analyzed using generalized linear model (GLM) procedures, which enable the use of non-Gaussian error models. Using a mixed-effects model in Mplus we will be able to estimate the main effect of the intervention considering the four time points nested within individuals allowing for time-varying effects of covariates to vary with time for the daily data collected.

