Primary hypothesis 2: Within-person mediational pathways will be found between participation in the intervention and PA and changes in DD on 2a) a daily basis (EMA) and 2b) over longer-time periods (1- and 2month change predicting PA outcomes at 4 months). Using mixed-effects mediation modeling assuming time points clustered within individuals with Mplus and mediation package from R[104-107], we will test how the relationship between intervention condition and PA is mediated by change in DD over time by using daily data and also running prediction models by the four time points. DD will be evaluated for normality and linearity assumptions and if assumptions are violated, GLM models will be established to determine the indirect effect.

Exploratory hypothesis: Environmental context will moderate the mediational pathways such that DD will be a stronger determinant of behavior in environments with more proximal costs. A moderated mediation mixedeffects model will test the strength or weakness of the indirect effect and/or the direct effect of the intervention condition on PA by the different environmental factors measured. The mixed-effects will consider effects by the daily data collected within the four general time points nested within individuals.

Missing data. We will run a systematic analysis of missing EMA data to determine whether the likelihood of response at any given prompt is time-varying (e.g., time of day/week, activity level). We anticipate approximately ~80% of prompts will be answered⁷⁵. If needed, we will use multilevel data imputation strategies ⁹⁴. For clinicbased data, type of missingness will be evaluated and values will be imputed using full information or restricted maximum likelihood estimation ⁹⁵. All variables in our models will be used to impute missing data. Sensitivity analyses will be used to compare results with and without imputed values.

Inclusion/Exclusion Criteria.

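### The hypothesis 1 model is worded as a main effect over four visits, one of them before randomisation, with no contrast or baseline handling stated; taken literally it estimates 0.75d, with about 58% power at 30 per arm against the plan's 82.1%

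*Combined protocol and SAP*

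**What the plan says.** Under Analyses, Primary hypothesis 1, the mixed-effects model is to "estimate the main effect of the intervention considering the four time points nested within individuals", and the sentence continues "allowing for time-varying effects of covariates to vary with time for the daily data collected". The Power paragraph uses d = 0.50, two-sided alpha 0.05 and the same visit count: "The computations assume an intraclass correlation (ICC) of 0.250 for the 4 time points clustered within each participant". It reports 82.1% power but not the number analysed.

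The Delayed Discounting and Physical Activity (Primary Outcome) sections place both outcomes at Phase II months 0, 1, 2 and 4. The Randomization section requires the Phase II baseline measures to be complete before allocation.

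The baseline rule for the main model concerns demographics: "if differences on any of the demographics are found at baseline, the variable will be used as a covariate in the main model". WAIS-II is listed among the covariates, and of Spot-the-Word the plan says "It will be utilized as a covariate in analyses to clarify the relative contribution of global vs. specific cognitive abilities on outcomes". None of these is baseline activity or baseline discounting. Arm comparisons by "t-test (means) at each time point" are also planned. For missing clinic data, "values will be imputed using full information or restricted maximum likelihood estimation".

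**The concern.** A main effect of arm in a model of all four visits is the arm difference averaged over those visits. Randomisation makes the expected difference at month 0 zero, so the average is pulled towards zero. An analyst who follows the sentence would report a follow-up effect about a quarter too small and would run a higher risk of missing a real one. The type I error rate is unaffected.

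The rest of the sentence does not rescue the contrast. It speaks of covariate effects in daily data, not of an arm-by-time term. If the daily data are the EMA data, they are collected "at Phase II 0, 2, and 4-month assessments", which is three waves and not four. Hypothesis 2 uses change in discounting, but in the mediation model.

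Because the contrast is not named, several analyses fit the text and give different estimates and different power. The choice could then be made after the data are seen.

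**Working it through.** **Inputs.** From the Power paragraph: d = 0.50, ICC 0.25, four time points, equal SDs (set to 1), two-sided alpha 0.05. From the Overview: 70 randomised. The attrition allowance is 15%.

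**Assumptions.** Allocation is 1:1. Correlations between visits are equal. The effect is d = 0.50 at each of months 1, 2 and 4. The analysed N is not stated: 70 × 0.85 = 59.5 suggests about 30 per arm, and 35 per arm (all 70) is shown beside it. Power uses the noncentral t.

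**Step 1: reproduce 82.1%.** Variance of a participant's four-visit mean = (1 + 3 × 0.25)/4 = 0.4375. SE of the arm difference = √(0.4375 × 2/n) = 0.1708 at n = 30 and 0.1581 at n = 35. With the full 0.50 at all four visits, power is 82.09% at 30 per arm and 87.6% at 35. The plan's figure is matched at 30 per arm.

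**Step 2: set month 0 to zero.** Mean effect = (0 + 0.50 + 0.50 + 0.50)/4 = 0.375 = 0.75d, with the same SE. A generalised least squares fit with visit effects gives the same coefficient (0.375) and SE (0.1708).

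**Step 3: three follow-ups adjusted for baseline.** Variance of the three-visit mean = (1 + 2 × 0.25)/3 = 0.50. Its covariance with baseline is 0.25, so the adjusted variance = 0.50 − 0.25² = 0.4375. The SE is again 0.1708 at n = 30, but on the full 0.50.

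| Analysis | Effect | Power, 30 per arm | Power, 35 per arm |
|---|---|---|---|
| Full d at all four visits | 0.50 | 82.1% | 87.6% |
| Literal main effect, month 0 zero | 0.375 | 57.9% | 64.7% |
| Months 1, 2, 4 adjusted for baseline | 0.50 | 82.1% | 87.6% |
| Months 1, 2, 4 unadjusted | 0.50 | 76.8% | 83.1% |
| t-test at one visit | 0.50 | 47.8% | 54.1% |

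The loss against the baseline-adjusted analysis is 82.1 − 57.9 = 24.2 points at 30 per arm and 87.6 − 64.7 = 22.9 at 35. Simulation (20,000 runs per N) agrees: the literal test averages 0.375 and 0.376 with power 57.8% and 64.9%; the adjusted one averages 0.499 and 0.501 with 81.4% and 87.3%.

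**Step 4: what would restore the power.** Either the follow-up d must be 0.50/0.75 = 0.667, or about 53 per arm are needed at d = 0.50 to reach 82.1%.

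**Step 5: attrition.** Take 35 per arm at month 0 and 30 at month 4, with all available data used by likelihood.

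- Losses spread evenly: the literal test estimates 0.361 (SE 0.162, power about 59%); the equal-baseline model estimates 0.500 (SE 0.165, about 85%).
- All losses right after month 0: 0.350 (SE 0.165, about 55%) against 0.500 (SE 0.171, about 82%).

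Dropout makes the dilution worse, because month 0 is then the fullest visit.

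**The case against.** The strongest reply is that the sentence describes a class of model and does not write out a test. Main effect may simply mean the overall treatment effect, and many statisticians would adjust for baseline unprompted. The 82.1% fits a baseline-adjusted follow-up analysis as well as it fits the four-visit mean. It also stands if d = 0.50 was meant as the four-visit average. All of this is fair, and it is why 58% belongs to the literal reading only. But the plan says none of it, and the four-visit-average definition requires a follow-up difference of 0.667.

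A second reply is that the daily data may be accelerometer days, since the device is worn for seven days at all four visits. The single-ICC variance would then not apply. That limits the power figures, but such a model would still pool the pre-randomisation visit. Nor do the figures carry over to the non-Gaussian model that the plan allows for activity.

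Third, the t-tests at months 1, 2 and 4 would show undiluted differences. They would, but each has only 48% to 54% power, is unadjusted for baseline, and is not the main model.

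**Conclusion.** The concern holds. The main model for a primary hypothesis is worded so that a pre-randomisation visit enters the treatment effect, and nothing in the plan removes it. Read literally, it estimates 0.75d and has about 58% power at 30 per arm, or 65% at 35. A baseline-adjusted analysis of the same data has 82% and 88%. At 30 per arm the chance of missing a true d of 0.50 rises from about 18% to 42%.

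These figures rest on a constant d over the three follow-ups, ICC 0.25, equal correlations, complete data and an inferred analysed N. They cover only the four-visit outcomes, activity and clinic discounting. An effect that builds or fades would change the factor of 0.75. Because the text is ambiguous, the 82.1% is unsupported for the literal test rather than wrong for every reading. The wording should be fixed; confidence is medium.

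**What to change.** - State the primary contrast for activity and for clinic discounting: outcomes at months 1, 2 and 4, the Phase II baseline value of the same outcome as covariate, and the condition effect averaged over the three follow-ups. Equivalently, keep four visits and constrain the arm means to be equal at month 0.
- Describe the EMA daily-data model in its own sentence, with its three waves.
- Restate power for the chosen model, saying what d refers to and how many are analysed. With d = 0.50 at each follow-up and ICC 0.25, this is about 82% at 30 per arm and 88% at 35.

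The cost is a rewording of the Power and Primary hypothesis 1 paragraphs. The baseline values are already collected, and no participants or visits are added.

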Randomization. Participants who lose $\geq 5\%$ during Phase I, agree to participate in Phase II, and complete Phase II baseline measures will be randomized to WLM-HT or WLM+FT. The statistician will use a permuted block randomization scheme for each cohort, stratified by initial weight loss (5-10% vs. $\geq 10\%$) and age (18.0-34.9, 35.0-59.9 and 60.0 years old and above).

Treatment Components Common to Both Conditions. Both WLM-HT and WLM+FT will involve a 4- month group-based WLM program consistent with current best practice^{50,65}. Sessions will taper over time; weekly for two weeks, every other week for six weeks, and once a month for two months (7 sessions total). Intervention contact time will be matched across groups to approximately 60-90 minutes per session. All treatment groups will be conducted at our office on the 6th floor of [name].

Interventionists. Two interventionists will co-deliver treatment. Interventionists will be trained by the P.I. At least one of the two interventionists will be master's level in a related field.

In-person treatment sessions. Note: In the event of a national emergency (e.g., COVID-19), sessions will be conducted remotely via a video conferencing platform like WebEx. Participants will be weighed privately by interventionists at each session. Given evidence that most individuals do not recover from even small amounts of weight regain⁶⁶, participants will be given the goal to keep their weight at or below their Phase II baseline weight (i.e., maintain their initial weight loss in full). Participants will be provided evidence-based weight loss maintenance strategies to meet this goal, including calorie guidelines, a physical activity plan, and behavior change skills associated with optimal weight maintenance. These components are detailed below.

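### Both arms are treated in groups, but the power calculation and main models cluster only visits within persons, so the stated 82.1% power holds only if the treatment-group ICC is zero

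*Combined protocol and SAP*

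**What the plan says.** Under Treatment Components Common to Both Conditions, each arm receives a 4-month "group-based WLM program consistent with current best practice". There are seven group sessions, co-delivered by two interventionists. The Overview plans two cohorts, with at least 35 randomised from each. Randomization is of individuals, in permuted blocks within cohort.

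The Power paragraph states that "power is computed for an effect size (d) of 0.50", with "an intraclass correlation (ICC) of 0.250 for the 4 time points clustered within each participant". It adds: "The standard deviation is assumed to be the same in the two conditions". On the test it says: "The criterion for significance (alpha) has been set at 0.05" and "The test is 2-tailed, which means that an effect in either direction will be interpreted". From these inputs, "the study will have 82.1% power to yield a statistically significant result".

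Under Primary hypothesis 1, the mixed model is to "estimate the main effect of the intervention considering the four time points nested within individuals". The mediation model (Primary hypothesis 2) and the moderated mediation model (Exploratory hypothesis) use the same nesting. Nowhere do the documents give a treatment-group or interventionist effect, a cluster-robust standard error, a group ICC, a number or size of groups, or a reason for leaving groups out.

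**The concern.** People treated in the same group share peers and session experience for four months, and group meetings are seven of the nine in-person treatment sessions. Their outcomes may therefore be correlated even though they were randomised individually. If each group belongs to one arm, variation between groups adds to the variance of the difference between arms. A model that nests only visits within persons leaves that component out.

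The arm comparison on physical activity and delay discounting would then have a standard error that is too small, an interval that is too narrow and a type I error above the nominal 5%. The power figure would be too high for the same reason. With about 35 randomised per cohort the groups must be few, so each would hold an appreciable share of its arm.

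**Working it through.** **Inputs from the documents.** d = 0.50, visit ICC 0.25, four time points, two-sided alpha 0.05 and equal SDs (Power); 70 randomised in two cohorts (Overview); 15% attrition (Power).

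**Derived.** 70 × 0.85 = 59.5, taken as 60 analysed. Equal allocation is assumed, since the ratio is not stated, which gives 30 per arm.

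**Assumed.** Arm-specific groups. Either one group per arm per cohort (4 groups, 30/2 = 15 completers each) or two (8 groups, 30/4 = 7.5 each). Group ICC of person means 0.01, 0.03 or 0.05. None of these values is in the documents.

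**Step 1: reproduce 82.1%.**
- Repeated-measures design effect: 1 + (4 − 1) × 0.25 = 1.75.
- Variance of a person mean, in SD units: 1.75/4 = 0.4375.
- SE of the arm difference: √(2 × 0.4375/30) = 0.1708.
- Noncentrality: 0.50/0.1708 = 2.928. Noncentral t with 58 df gives 82.09%.

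This matches the stated figure with nothing left over for groups. All 35 per arm would give 87.6%, so 82.1% is already net of attrition.

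**Step 2: add a group effect.** Group design effect DE = 1 + (g − 1) × ICC, with g completers per group. The true SE is 0.1708 × √DE. Type I error of the planned test is 2 × [1 − Φ(1.96/√DE)]. Power uses noncentrality 2.928/√DE with 58 df.

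| Groups (g) | ICC | DE | SE ratio | Type I error | Power, 58 df |
|---|---|---|---|---|---|
| 4 (15) | 0.01 | 1.140 | 1.07 | 6.6% | 77% |
| 4 (15) | 0.03 | 1.420 | 1.19 | 10.0% | 68% |
| 4 (15) | 0.05 | 1.700 | 1.30 | 13.3% | 60% |
| 8 (7.5) | 0.01 | 1.065 | 1.03 | 5.8% | 80% |
| 8 (7.5) | 0.03 | 1.195 | 1.09 | 7.3% | 75% |
| 8 (7.5) | 0.05 | 1.325 | 1.15 | 8.9% | 71% |

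The result depends on the scale of the ICC. If it is defined for single observations instead of person means, the variance of an arm mean is [0.4375 + (g − 1) × ICC]/30. Power is then 70.7% to 76.6% at ICC 0.01 and 43.1% to 58.7% at 0.05 (4 to 8 groups).

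**Step 3: power of an analysis that respects groups.** With a group random intercept and fixed effects for arm and cohort, group-level df are groups − 3, that is 1 or 5. At the same noncentralities, power at ICC 0.01 / 0.03 / 0.05 is about 17 / 15 / 14% with 4 groups and 63 / 58 / 54% with 8.

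**The case against.** The strongest reply is that the harm is conditional. It needs a positive group ICC and arm-specific groups, and the documents establish neither. Group delivery is listed among the components common to both arms. Much of what separates the arms is individual: two case-management visits, weekly calls and website cues. At the mild end (8 groups, ICC 0.01) the figures are 5.8% and 80%, close to immaterial. All of this stands as a limit on size. On arm-specificity, the WLM+FT section places cue generation at each session, and Treatment fidelity checks session recordings for contamination between arms. Both make separate groups likely, but it remains an inference.

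A reader might infer that group is fully confounded with arm. That would be true only with one group per arm per cohort, and the number of groups is not stated. With two or more, groups are nested in arm and their variance can be estimated.

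A reader might also count shared timing and shared leaders as sources of bias. The documents do not support this. Cohort is crossed with arm because randomisation is blocked within cohort, and nothing says that the leaders differ by arm. What clearly remains is the effect of peers and of the sessions themselves.

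Two further points moderate the size. Groups form after baseline, so clustering acts mainly on three of the four time points. The model also names none of the stratification factors, and leaving those out tends to make the standard error too large, a partial offset that the documents do not allow one to quantify.

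Finally, a variance component from 4 groups is barely estimable. That is a fair argument against making such a model primary in that case. It does not justify a silent assumption of zero.

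**Conclusion.** The omission is real and can be read directly from the plan: the 82.1% is power at zero group ICC, and the models carry the same assumption without stating it. Other things equal, and with arm-specific groups, any positive group ICC makes the planned standard error too small and the stated power too high.

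On the completer basis and for person-mean ICCs of 0.01 to 0.05, type I error ranges from about 6% to 13% and power with person-level df from about 80% down to 60%. Those ranges rest on assumed ICCs and group counts. They do not show that the trial's actual error rate is any particular figure. If the group ICC were zero, the planned standard error would need no correction on this account.

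**What to change.** 1. Record each participant's treatment group, and state in the protocol how many groups are planned and whether each serves one arm only.
2. In the Power paragraph, label 82.1% as power at zero group ICC, give the completer number behind it, and show power over ICC 0.01 to 0.05 at the planned number of groups.
3. Under Primary hypothesis 1, include cohort as a fixed effect. Pre-specify an analysis of physical activity and delay discounting with a random intercept for treatment group (nested in arm and cohort) and small-sample df (Kenward-Roger or Satterthwaite).
4. Make that analysis primary if there are enough groups, for example 8. Otherwise make it a sensitivity analysis. In either case report the group ICC and interpret the arm effect in light of it.

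The cost is SAP wording and one extra variable, which may not be recoverable if it is not captured during delivery. No more participants are needed to make the change. The downside is that stated power becomes less favourable, intervals widen and group-level inference is weak, very much so with 4 groups. That is why the choice between primary and sensitivity analysis should depend on the number of groups and be fixed in advance.

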Physical Activity (Primary Outcome). The validated^{83,84} Actigraph GT9X will be worn on the waist for 7-days at Phase II 0,1, 2, and 4 months. Data will be processed with the ActiLife software, ensuring wear time requirements and validated algorithms. Time spent in MVPA and bout-related MVPA (≥ 10 min in duration) will be examined. In addition, following [name] et al.’s protocol that has been validated against accelerometry^{75,77}, each EMA prompt will include questions about activity type and purpose that cannot be captured by accelerometers. To allow for future direct comparisons of Phase I processes, we will also administer the Paffenbarger (PAQ)^{62,63}.

Weight (Secondary Outcome). Weight will be measured to the nearest 0.1kg with a digital scale. Participants will be measured wearing one layer of clothing without shoes. Weight will also be measured objectively at each WLM session and reported over the phone to case-managers on a weekly basis.

Environmental Context (Moderators). EMA measures of the environment focus on factors that may alter the cost/benefits of PA. On each EMA prompt, participants will be asked to indicate their current physical and social context. Following Elliston et al.²⁴, participants will be asked whether they can see others in their environment being physically active (**norms**), whether a TV or computer can be seen from where they are sitting/standing (**sedentary options**), and whether exercise equipment is available or if they are within a 5- minute walk to a place they can be physically active (**accessibility**). We will then ask, consistent with Booker & Mullan⁸⁵, about 5 potential PA triggers (physical, sensory, social, internal, and external drives; e.g., “Right now, are there any social triggers in the environment which are influencing your physical activity”). The mean of the 5 items will be used to create an **environmental responsiveness** score. Consistent with other EMA protocols⁸⁶, **stress** will be assessed with 3-items of the Perceived Stress Scale⁸⁷ adapted for momentary use (e.g., “How stressed do you feel right now”) and **social support** will be measured with 1-item⁸⁸. Local **weather** indices will be obtained for the EMA dates from a national weather service, as we have done in a prior study⁸⁹.

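### Hypothesis 2b gives no model equation and no month-0 DD or PA term; on its natural reading the indirect effect ranges from unbiased to about 75–80% attenuated

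*Combined protocol and SAP*

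**What the plan says.** Under Analyses, Primary hypothesis 2, part 2b is described as "1- and 2month change predicting PA outcomes at 4 months". The method is mixed-effects mediation with time points clustered within people, with daily-data models and prediction models using the four time points. No equation is given. The predictor is called a change; the PA outcome is tied to a month and not called a change.

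The covariate rules do not bring in the baselines of the mediator or outcome. Under Primary hypothesis 1, demographics that differ between arms at baseline enter the main model. An intelligence measure is also named as a covariate. Neither rule covers month-0 DD or month-0 PA.

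Both are collected. The DD task is given "at the start of weight loss maintenance and 1, 2, and 4 months later" (Delayed Discounting), and the accelerometer "will be worn on the waist for 7-days at Phase II 0,1, 2, and 4 months" (Physical Activity). The Randomization section requires completed Phase II baseline measures before allocation, so every randomised participant should have both values.

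**The concern.** A change score carries the baseline value with a minus sign. If month-4 PA depends on where DD stands at follow-up, variation in month-0 DD adds noise to the predictor and pulls the slope towards zero. If baseline DD and PA are also related, and PA is stable over time, the pull is stronger. The lost part of the indirect effect then appears as a direct effect.

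A random person effect does not repair this. A model in which 1- or 2-month change predicts month-4 PA has one outcome value per person, so there is no repeated outcome from which to remove stable differences.

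This is part of a primary hypothesis, tested in about 60 completers. Leaving the equation open also leaves a choice, after the data are seen, between models that can give very different indirect effects.

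**Working it through.** **Inputs from the documents (Power and Overview).** Alpha is 0.05, two-sided. On the size of effect, "power is computed for an effect size (d) of 0.50". For the repeated measures, the plan takes "an intraclass correlation (ICC) of 0.250 for the 4 time points clustered within each participant". Equal SDs are assumed in both arms. N = 70 randomised; 15% attrition leaves 70 × 0.85 = 59.5, about 30 per arm if allocation is 1:1 (the ratio is not stated).

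**The plan's own figure.** The SD of a participant's mean over four time points is √((1 + 3 × 0.25)/4) = 0.661. With a difference of 0.5 and 30 per arm, power is 82.1% by the noncentral t (83.3% by normal approximation). The stated 82.1% therefore reproduces, but it is power for the arm comparison. No power is stated for the indirect effect.

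**Assumptions that are not in the documents.** DD has SD 1 at both times, with retest correlation ρ. The arm effect on DD is a = 0.5 SD (taking d = 0.50 as this path). The DD-to-PA path is b. Month-4 PA depends on month-0 PA with coefficient g = 0.5. Baseline DD and PA correlate r₀ = 0 or 0.3, in the same direction as b. There is no direct effect. Signs are dropped below.

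**Slope of month-4 PA on D = DD(follow-up) − DD(0), given arm only.** Within arm, var(D) = 2(1 − ρ) and cov(D, PA₀) = −(1 − ρ)r₀.

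- *Follow-up level drives PA*, PA₄ = b·DD(follow-up) + g·PA₀ + error: cov(D, PA₄) = (1 − ρ)(b − g·r₀), so the slope is (b − g·r₀)/2 for any ρ.
- *Change drives PA*, PA₄ = b·D + g·PA₀ + error: the slope is b − g·r₀/2.

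The arm effect on DD change is unbiased in both cases, so the indirect effect is scaled by the same ratio as the slope. With g·r₀ = 0.5 × 0.3 = 0.15:

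| Cause of PA | r₀ | b = 0.3 | b = 0.4 | Ratio to truth, simulated |
|---|---|---|---|---|
| DD change | 0 | 0.30/0.30 = 1.00 | 0.40/0.40 = 1.00 | 0.98–1.03 |
| DD change | 0.3 | 0.225/0.30 = 0.75 | 0.325/0.40 = 0.81 | 0.74–0.82 |
| DD level | 0 | 0.15/0.30 = 0.50 | 0.20/0.40 = 0.50 | 0.48–0.51 |
| DD level | 0.3 | 0.075/0.30 = 0.25 | 0.125/0.40 = 0.31 | 0.24–0.32 |

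A separate run with b = −0.3, ρ = 0.5 and baselines correlated −0.3 gave a slope of −0.07, an attenuation of 1 − 0.07/0.30 = 77%.

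**With month-0 DD and month-0 PA added,** the simulated indirect effect was 0.98–1.02 of its true value in every setting (ρ from 0.25 to 0.85, b of 0.3 or 0.4, N = 60 or 70).

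**Power** (both paths significant at two-sided 0.05, N = 60, size of b shown):

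| Setting | No baselines | Both baselines | Ratio |
|---|---|---|---|
| Level drives PA, ρ = 0.5, b = 0.4, r₀ = 0 | 15.4% | 54.0% | 0.29 |
| Level drives PA, ρ = 0.5, b = 0.3, r₀ = 0.3 | 3% | 35% | 0.09 |
| Level drives PA, ρ = 0.25, b = 0.5, r₀ = 0 | 23% | 48% | 0.48 |
| Change drives PA, ρ = 0.5, b = 0.4, r₀ = 0 | 41.5% | 51.6% | 0.80 |

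Across all settings the ratio ran from about 0.1 to about 0.9. Adjusted power itself was only 0.25–0.73.

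**Stable trait.** If a stable trait also drives PA and true b is −0.30, the adjusted slope is −0.34, slightly too large; PA change on DD change gives −0.30. That alternative is not safe everywhere: when DD change drives PA and the baselines correlate 0.3, it came out about 1.2 times too large.

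**The case against.** The strongest reply is that no such regression is written down. The quoted words sit in a hypothesis statement. The method sentence names a within-person, mixed-effects analysis over four time points that include month 0, and the Power section expects covariates in the models. Silence on baseline terms does not exclude them. This stands: the plan is under-specified rather than demonstrably wrong, and level-on-change is the natural reading but not the only one.

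A reader might infer that the plan halves the indirect effect and cuts its power to about a third. The documents do not support that as a general statement. Halving requires that follow-up DD level drives PA, that DD variances are equal and that baseline DD and PA are unrelated. The protocol's theory can be read that way, but its introduction also cites change in executive function predicting later activity, and hypothesis 2 is framed around change in DD. Under change causation with unrelated baselines there is no bias at all.

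It is also fair that some of the power gain is ordinary precision from baseline PA. With correlations of 0.7 and b = −0.3, one run gave about 29% with month-0 DD alone and 50% with month-0 PA added. And the adjusted model would itself often miss a path of this size.

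None of this is a reason to leave the baselines out. The adjusted model recovered the slope, and beat the unadjusted one on power, under both level and change causation.

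**Conclusion.** The point holds as an under-specification with a concrete and nearly free improvement. On the natural reading of 2b, the DD-to-PA slope and the indirect effect range from unbiased, through one half, to roughly 75–80% attenuated. Power is about 0.1 to 0.9 of that of the baseline-adjusted model. No single figure in that range can be called the plan's error, because the documents give no retest correlation, path size or baseline DD–PA correlation. The range also assumes that any baseline correlation runs in the direction the theory predicts; the opposite sign would move the bias the other way. What does not depend on these values is the action: with no stable trait at work, adding both baselines removed the bias in every setting examined, and where a trait does drive PA the remaining bias was small.

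**What to change.** Write out the 2b model:

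- Mediator equation: DD change (month 1 or 2 minus month 0) on arm, month-0 DD and month-0 PA.
- Outcome equation: month-4 accelerometer PA on arm, DD change, month-0 DD and month-0 PA.

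State which accelerometer measure is the outcome (total or bout-related MVPA), and use the same one at month 0. Once month-0 DD is in the outcome equation, using the follow-up level instead of the change gives the same DD slope. Month-0 PA alone is not enough: with unrelated baselines and level causation the slope stays at one half.

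Add PA change (0 to 4 months) on DD change as a sensitivity analysis, because the adjusted slope can be slightly too large if a stable trait drives both. Keep it secondary, since it is biased under other models.

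In the same edit, reconcile the timing: the introduction gives 2b as 1- and 3-month change with PA at 6 months, whereas the Analyses section uses 1 and 2 months with PA at 4 months.

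The cost is a short addition to the plan and two degrees of freedom. No new data are needed.
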